8.1. General Methods

SAS® version 9.4 or higher will be used for all statistical analyses and tabulations.

In general, summaries will present data by treatment group and overall for each scheduled assessment time where appropriate. Efficacy, PK and PD summaries will be presented by treatment group, only.

Unless stated otherwise, descriptive summaries will be presented as follows: Continuous and ordinal variables will be summarized by the number of patients (N), mean, standard deviation, median, minimum, and maximum for actual values and change from baseline. Additionally, for ordinal data, the number and percentage of patients in each category will be presented. Binary and categorical variables will be summarized by treatment group by presenting the number and percentage of patients in the categories.

Statistical tests for comparison between treatments for all defined estimands and endpoints of efficacy will be performed using a two-sided alpha level of 10%. No adjustment for multiple testing will be applied in this descriptive proof-of-concept study. Additionally, 95% confidence intervals will be provided.

Adverse events and medical history will be coded according to the most recent version of Medical Dictionary for Regulatory Activities (MedDRA). Prior and concomitant medications will be coded using the most recent WHO Drug Dictionary version. The actual version of MedDRA and WHO drug used will be noted in the footnote of the respective output. Unless otherwise specified, summaries will be presented for each treatment and overall.

If there are multiple assessments collected for the same scheduled time, the last available assessment before start of study treatment will be used as baseline value and the first assessment at the respective post-baseline visit will be used for post-baseline summarization, except for COVID-19 test results where the last assessment at the post-baseline visit will be used for post-baseline summarization.

All relevant patient data will be included in listings. All patients entered into the database will be included in patient data listings.

Data collected at unscheduled visits will be included in the data listings but will not be included in the analyses or in treatment summaries except unscheduled COVID-19 test results.

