- g. Medical/surgical medical history includes all active and chronic diseases (eg, asthma and COPD), and any diseases diagnosed in the past 1 year (before screening) that the investigator considers clinically significant. Additional pre-existing conditions present at the time when informed consent is given and up to the time of first dosing (Day 1) are to be regarded as concomitant. Medical history will include documentation of social behaviors, including use of tobacco, nicotine (including use of electronic cigarettes), and soft or hard drugs (including cannabis), as well as alcohol consumption, if applicable. Smoking history also must be documented as part of medical history and includes: never, light (<100 cigarettes/lifetime), active smoker, and former smoker (quit date). History of number packs/day, number of smoking years, and quitting time for former and active smokers must also be documented. Additionally, the investigators will document at screening the patient's Charlson score via the Charlson Comorbidity Index (see Section 12.1 of protocol for further details).

- h. A complete physical examination will be performed at screening. Physical examinations will be performed by a physician, nurse, or other appropriately trained staff. The complete physical examination includes: head, eyes, ears, nose, and throat; heart; lungs; abdomen; skin; cervical and axillary lymph nodes; and neurological and musculoskeletal systems. A limited physical examination to verify continued patient eligibility and to follow-up regarding any change in medical history will be performed at the visits indicated above. Symptom-driven, limited physical examinations may be performed as clinically indicated during the study (according to SoC).
- i. Vital signs include systolic and diastolic blood pressure, heart rate, respiration rate, SpO₂, and body temperature. All vital signs will be measured after the patient has been resting for at least 5 minutes. Blood pressure measurements are to be taken in the same arm for the duration of the study. Moreover, additional vital signs may be performed as needed in case of any cardiac AE.
- j. For patients who remain hospitalized only.
- k. A 12-lead, resting ECG will be obtained locally at screening. At screening, the investigator must examine the ECG traces for clinically significant abnormalities that could exclude the patient from the study. ECGs should always be obtained in supine position after adequate rest (≥5 minutes).

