13.2. Laboratory Evaluations

Clinical laboratory data of local laboratories will be presented in separate tables for each laboratory test type (hematology, blood chemistry, coagulation, urinalysis). Each laboratory parameter will be presented with the number and percentage of patients with values below, within, or above the normal range at each time point by treatment group and overall. Additionally, a shift table of the number and percentage of patients with values below, within, or above the normal range at each time point by treatment group and overall. Additionally, a shift table of the number and percentage of patients with normal and abnormal, and clinically significant abnormal values at each scheduled post-baseline visit compared to the normal, abnormal, and clinically significant abnormal categorization at baseline will be provided by treatment group. A listing of clinically significant abnormal values will be provided in the tables section.

Summary tables of actual values and changes from baseline can be presented for continuous laboratory parameters only after 'normalization' of the local laboratory assessment as supposed by Chuang-Stein (see reference 1 and 2) using one reference laboratory based on the following formula

$$s = L_s + (x - L_x) \frac{U_s - L_s}{U_x - L_x}$$

where s = the transformed individual laboratory value considering the normal range of the reference laboratory, x = the original laboratory value, L_x and U_x are the lower and upper limits or normal range of the local laboratory for the respective parameter, L_s and U_s are the lower and upper limits of the selected reference laboratory. For calculating summary statistics, results of <x or <=x will be imputed as x/2 and results of >x or >=x will be imputed as x.

Pregnancy test results will be listed only for randomized female patients.

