13.3. Vital Signs

Vital signs will include systolic blood pressure (mmHg), diastolic blood pressure (mmHg), heart rate (beats per minute, bpm), respiration rate (breaths per minute), SpO₂, and body temperature (°C). Summary tables of the actual values and changes from baseline will be provided for each vital sign parameter at each scheduled visit by treatment group, and in total.

Additionally, body weight and BMI will be summarized with actual values and change from baseline at each scheduled visit by treatment group, and in total.

Vital signs data, body weight and BMI will be listed for randomized patients.

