13.5. Physical Examination

Abnormal physical examination results will be summarized by presenting number and percentage of patients for each body system by treatment group and overall for all scheduled visits. All physical examination data will be listed for the randomized patients.

This document is confidential.

SAP Text Version: 2.0, 31-Aug-2022 Controlled Document ID: CC , Effective Date 31-Aug-2020 Filing requirements: TMF

Page 46 of 56

14. Health Economics

Not applicable.

This document is confidential.

SAP Text Version: 2.0, 31-Aug-2022 Controlled Document ID: CC , Effective Date 31-Aug-2020 Filing requirements: TMF

Page 47 of 56

15. Interim Analyses or IDMCs

There will be no interim analysis in the study.

An independent DMC will be established by the sponsor or designee to review accumulating study data at regular intervals (as per the DMC charter) throughout the study to ensure the safety of patients and review overall study conduct. Additional data may be reviewed that are related to efficacy, but the DMC will only be reviewing data for risk-benefit purposes. Members will include experts in drug safety and/or medical specialist and biostatistics, who are not participating in this study and do not have affiliation with the investigators or the sponsor. The DMC can recommend in writing to the sponsor whether to continue, modify, or stop the clinical study on the basis of safety considerations. The pre-specified study stopping rules for the trial are defined as follows:

- death (not including disease progression) in any patient in whom the cause of death is judged to be related to the study drug by investigator
- the occurrence in any patient of a SAE whose causal relationship (ie, without a plausible alternative explanation) to the study drug is judged to be related by investigator
- two occurrences of a clinically significant Grade 3 or higher laboratory abnormality assessed to be related to the study drug by investigator.

The DMC's specific duties will be fully described in a DMC charter. The list of the outputs that will be produced for the DMC will be attached to the charter. An unblinded team from Syneos Health Biostatistics will perform the analyses as described in Section 4.4 of this SAP to maintain the blinding of the study.

This document is confidential.

16. Changes from Analysis Planned in Protocol

Not applicable

This document is confidential.

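### Event-triggered laboratory, vital-sign and examination values stay in listings, because the SAP plans no worst-post-baseline or any-time safety summary by arm

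*SAP*

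**What the plan says.** Section 8.1 sets the general rule: "Data collected at unscheduled visits will be included in the data listings but will not be included in the analyses or in treatment summaries". The sentence closes with its one exception, "except unscheduled COVID-19 test results". The same section deals with several assessments at one scheduled time: "the first assessment at the respective post-baseline visit will be used for post-baseline summarization", again with a different rule for COVID-19 tests.

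The safety sections do not override this:

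- **Laboratory (13.2).** The shift table covers "clinically significant abnormal values at each scheduled post-baseline visit compared to the normal, abnormal, and clinically significant abnormal categorization at baseline". The counts below, within and above the normal range are given per time point and remain under the 8.1 exclusion. In addition, "A listing of clinically significant abnormal values will be provided in the tables section".
- **Vital signs (13.3).** Summaries are given "for each vital sign parameter at each scheduled visit by treatment group, and in total".
- **Physical examination (13.5).** Abnormal results are counted by body system at the scheduled visits.

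Table 1 in section 4.6 expects measurements outside this schedule. Footnote i says that "additional vital signs may be performed as needed in case of any cardiac AE", and footnote h allows limited examinations driven by symptoms. Section 5.7 names vital signs, clinical laboratory parameters and examination findings as safety endpoints, separate from adverse events.

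**The concern.** A value measured because a patient became unwell is selected for being informative, and the 8.1 rule removes such values from every summary of measured values by arm. By-visit tables can reasonably use scheduled data alone, since mixing in extra values would distort means and denominators. The usual complement is a table of the worst value, or of any abnormality after baseline, that draws on all results. The SAP plans neither.

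The omission sits oddly with how the SAP treats other safety data. Section 8.3 handles incomplete safety dates conservatively, and section 13.1 gives an adverse event recorded in several episodes its worst severity. Measured values instead count only if scheduled.

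At stake is the sensitivity of the between-arm comparison for three stated safety endpoints. A short-lived laboratory abnormality that is more frequent in one arm could be diluted or absent in the shift tables while it is visible in the listings. A reader could count it by hand, but that count would be unplanned and made after unblinding.

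**Working it through.** The SAP gives no figure on this point, so there is none to reproduce. The check reads the rules together and then illustrates the possible size for laboratory values.

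**Tracing a value through the plan.** Take a laboratory result from an unscheduled draw.

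1. Section 8.1 sends it to the listings and bars it from summaries; it is not a COVID-19 test.
2. The 13.2 shift table takes scheduled post-baseline visits only.
3. The 13.2 range counts and change-from-baseline summaries are also summaries, so 8.1 applies.
4. If judged clinically significant, the value can appear in the 13.2 listing, which gives no counts by arm.
5. It reaches a by-arm table only through 13.1, if it is reported as an adverse event.

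An extra vital-sign reading or a symptom-driven examination follows the same path through 13.3 or 13.5.

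**Inputs for the illustration.** From Table 1: laboratory draws after baseline for a patient in hospital on Days 8, 14, 21 and 28. Assumed: onset equally likely on each of Days 2 to 28 (28 − 2 + 1 = 27 days), draws exactly on the nominal day, discharge draw ignored, and durations of 3, 5 or 7 days.

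**Formula.** An abnormality of length L days starting on day d spans d to d + L − 1. A draw on day D detects it if D − L + 1 ≤ d ≤ D. Share missed = 1 − (detecting onset days / 27).

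- L = 3: onsets 6-8, 12-14, 19-21 and 26-28 are detected, 12 days. Missed: 15/27 = 56%.
- L = 5: onsets 4-8, 10-14, 17-21 and 24-28 are detected, 20 days. Missed: 7/27 = 26%.
- L = 7: onsets 2-8, 8-14, 15-21 and 22-28 are detected, which covers all 27 days. Missed: 0/27 = 0%.

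**Effect on a comparison (assumed rates, not from the SAP).** Suppose 15% of 80 patients on MP1032 (12) and 5% of 40 on placebo (2) have one clinically significant abnormality each, and detection is equal in both arms. The true difference is 15% − 5% = 10 points. In scheduled-visit tables it becomes:

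- 3-day: 10 × 12/27 = 4.4 points
- 5-day: 10 × 20/27 = 7.4 points
- 7-day: 10 × 27/27 = 10 points

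**Limits.** The missed shares bound what the 8.1 rule can cost in this setting. A missed abnormality is a loss from the tables only if an unscheduled test recorded it, and the discharge draw would catch some. The figures describe a patient with all four draws. After discharge, the Day 8 and Day 21 draws depend on clinical indication (footnotes s and u), so the figures do not carry over to those patients.

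**The case against.** The strongest reply is that adverse events already carry the harm. Section 13.1 counts any event starting or worsening after first dose up to Day 60, grades it by CTCAE version 5.0 and tabulates it by arm, whatever the visit. The extra vital signs in footnote i follow a cardiac adverse event, so that event is already counted. This stands as far as it goes. A reader might infer that triggered findings never enter any comparison by arm, and the SAP does not support that; it is true of the measured values only. But the adverse-event route depends on investigator reporting, and section 5.7 lists the measured parameters as endpoints in their own right.

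Other limits also stand:

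- Clinically indicated Day 8 and Day 21 laboratory tests after discharge belong to scheduled visits and can be summarized.
- Vital signs are scheduled across Days 2-13 for inpatients, so their gap is smaller, and no figure is offered for it.
- The rule taking the first of several values might look like a way to hide harm. Where an abnormal first value prompts the repeat, the rule keeps the abnormal one; it loses information only when the repeat is worse.
- Listings are sorted by treatment group (18.2.5.3), so with about 120 patients a hand count is possible. That reduces the harm but does not replace a planned table.

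A reader might also link the gap to the section 15 stopping rule, "two occurrences of a clinically significant Grade 3 or higher laboratory abnormality assessed to be related to the study drug by investigator", or conclude that the monitoring committee would be uninformed. Neither follows. The rule turns on clinical significance and an investigator's judgement of relatedness, and a table of worst grades carries neither. The committee's outputs are set in its charter, which is not at hand.

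**Conclusion.** The point holds for measured values. Followed as written, the SAP leaves unscheduled laboratory, vital-sign and examination results in listings and offers no by-arm summary that could include them. Triggered values count between arms only when they are also reported as adverse events.

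The size cannot be estimated from the SAP. For laboratory values in a patient drawn on all four days, the illustrated upper bound on loss runs from 0% (7 days) through 26% (5 days) to 56% (3 days). It rests on the assumed durations, uniform onset, exact draw days and no discharge draw.

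This is a modest gap in safety reporting. It affects no efficacy analysis, and it is no evidence that harm would go unrecorded.

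**What to change.** 1. Leave the by-visit tables in 13.2, 13.3 and 13.5 on scheduled data.
2. In 8.1, exempt safety parameters from the exclusion, and from the first-value rule, for worst-value summaries.
3. In 13.2, add a by-arm shift table from baseline to the worst post-baseline category, using every scheduled, unscheduled and repeat value in the database. Use CTCAE grade where it can be derived, otherwise the existing normal, abnormal and clinically significant classes.
4. In 13.3, add worst post-baseline vital signs by arm on the same basis.

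The cost is SAP wording and a few tables. Grading takes some derivation, because values come from local laboratories with different ranges; the fallback classes avoid this. Table 1 expressly requires unscheduled COVID-19 tests to be entered in the eCRF but says nothing similar for other unscheduled tests, so the new tables can cover only what was recorded.

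One downside remains: patients tested more often have more chances of an extreme value. Present the worst-value tables beside the scheduled-visit tables so that both can be read together.

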8.2. Key Definitions

Baseline is defined as the last non-missing value prior to the start date and time of the study drug. For non-treated patients, baseline is defined as the last non-missing value from the Screening and Day 1 visits.

Study Day 1 is defined as the first day of study drug administration. Study day will be calculated as date of event/collection – first dose date of the study + 1 for all assessments after start of study drug, and as date of event/collection – first dose date of the study for all assessments prior to start of study drug.

8.3. Missing Data

Missing data will be imputed for the primary efficacy and key secondary efficacy variables as described in sections 7 and 10.

Missing or incomplete dates in safety data: In all listings, missing or incomplete dates will be left as they have been recorded. However, for calculation and sorting based on dates and for consideration in summary tables, the following method will be used: The most conservative approach will be systematically considered

This document is confidential.

Page 31 of 56

(ie, if the onset date of an AE/concomitant medication is missing or incomplete, it is assumed to have occurred during the study treatment, ie, the AE will be considered as TEAE, except if the partial onset date indicates differently). A missing/incomplete date of medical history or disease diagnosis will be assumed to have occurred before any study treatment.

Missing TEAE relationship will be imputed by 'related' for summary tables.

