9.5. Medication

Prior medication is defined as any medication which has an end date prior to the date of first dose of study drug administration.

Concomitant medication is defined as any medication which starts before the last dose of study drug and has an end date after the date of first dose of study drug administration or missing.

The original verbatim terms collected in the eCRF for prior and concomitant medications will be coded using the World Health Organization Drug Dictionary (WHO-DD current version).

Listings will include the therapeutic (ie, the second level of Anatomical Therapeutic Chemical [ATC] classification system code that is corresponding to the first 3 figures), preferred name (the fourth level of the ATC code, that is, corresponding to the first 5 figures) and verbatim text. The listings will be sorted by treatment group, patient ID, chronological start date, stop date, therapeutic class, preferred name and verbatim name and will contain all randomized patients.

A frequency table of the number and percentage of patients will be provided for prior medications and concomitant medications by therapeutic class and preferred name for each treatment group and overall on the ITT.

Non-drug therapies collected on the eCRF will be listed and summarized by number and percentage of patients.

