13.1. Adverse Events / Adverse Drug Reactions

All AEs will be coded using the most recent MedDRA Version.

Each AE will be assigned a grade which refers to the severity of the AE based on the Common Terminology Criteria for Adverse Events version 5.0. The Common Terminology Criteria for Adverse Events v5.0 displays grades 1 through 5 with unique clinical descriptions of the severity for each AE. Tables for the classification of the AE severity and relationship to the drug are provided in Tables 6 and 7 in Section 12.6.1 of the protocol.

When changes in the severity of an AE occur more frequently than once a day, the maximum severity for the event should be noted in the eCRF. If the severity category changes over a number of days, then those changes should be recorded separately (with distinct onset dates) in the eCRF: the assessment of an AE in several records will be called as 'episodes' of one AE.

A treatment-emergent AE (TEAE) is an AE that starts or worsens at any time after initiation of study drug until the end of the follow-up period at Day 60. Events with missing onset dates will be considered as TEAEs. If a patient experiences >1 occurrence of the same AE, the occurrence with the greatest severity and the closest association with the study drug will be used in the corresponding summary tables. In case that for one AE, several AE episodes with eg changing severity are reported, an aggregation of all respective episodes to one AE will be performed prior to summarization. The worst severity and the worst relationship will be assigned to the aggregated AE.

Listings presenting all AEs including all episodes of one AE will be produced for TEAEs and non-TEAEs with the flagging of SAEs. Listings of serious TEAEs, TEAEs leading to study drug withdrawal, and TEAEs leading to death will be presented in the table section of the outputs. Additionally, in the listing TEAEs starting in the treatment period and TEAEs starting in the follow-up period or starting after the initial treatment has stopped will be flagged

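### The missing-onset rule for adverse events does not read the stop date, so an event recorded as over before the first dose would be tabulated as treatment-emergent

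*SAP*

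**What the plan says.** Section 8.3 sets a rule for undated or partly dated AEs: "if the onset date of an AE/concomitant medication is missing or incomplete, it is assumed to have occurred during the study treatment". It allows one exception: "the AE will be considered as TEAE, except if the partial onset date indicates differently". The rule does not alter the dates shown in listings. Its scope is "for calculation and sorting based on dates and for consideration in summary tables, the following method will be used".

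Section 13.1 restates the rule for wholly missing dates: "Events with missing onset dates will be considered as TEAEs". The same section gives the governing definition: "A treatment-emergent AE (TEAE) is an AE that starts or worsens at any time after initiation of study drug", with the period running to Day 60.

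Section 8.3 then adds a second imputation: "Missing TEAE relationship will be imputed by 'related' for summary tables".

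No section of the SAP uses an AE's stop date to decide whether the event is treatment-emergent. For medications, by contrast, section 9.5 does use the end date: "Prior medication is defined as any medication which has an end date prior to the date of first dose of study drug administration".

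**The concern.** A conservative imputation is meant to settle a case that the data leave open. When the onset is unknown but the stop date is known and precedes the first dose, the case is not open: the event was over before any study drug was given, so it can neither have started nor worsened after initiation. The rule as written still makes it a TEAE, because the only evidence it consults is the partial onset date.

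The second imputation builds on the first. If causality was left blank, the event is also tabulated as treatment-related.

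What is at stake is the accuracy of the safety tables. TEAE incidence is the first safety endpoint listed in section 5.7. Section 13.1 tabulates TEAEs and related TEAEs by treatment group. It also compares serious and related serious TEAEs between the groups by a ratio of exposure-adjusted rates with a 95% confidence interval. In addition, a programmer would have to choose between following the imputation rule and following the definition, and the SAP does not say which prevails.

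**Working it through.** The SAP states no figure on this point, so there is none to reproduce. The check applies the rule literally and then repeats it with one added condition.

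**Inputs from the SAP**
- Rule and single exception: section 8.3.
- Rule for wholly missing onset, and TEAE definition: section 13.1.
- Screening period of up to 7 days: section 4.1.
- Planned arm sizes of 80 (MP1032) and 40 (placebo): section 4.3.

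**Step 1: the rule as written.** An AE is a TEAE unless the latest date compatible with its partial onset is before the first dose. A wholly missing onset is always a TEAE.

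**Step 2: the rule with a stop-date condition.** As step 1, but an AE with a known stop date before the first dose is not a TEAE.

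**Step 3: test cases**, with an illustrative first dose on 15 March 2022.

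| Onset recorded | Stop recorded | As written | With stop-date condition |
|---|---|---|---|
| missing | 13 Mar 2022 | TEAE | not TEAE |
| 2022 only | 13 Mar 2022 | TEAE | not TEAE |
| Mar 2022 | 13 Mar 2022 | TEAE | not TEAE |
| Feb 2022 | 13 Mar 2022 | not TEAE | not TEAE |
| 13 Mar 2022 | 13 Mar 2022 | not TEAE | not TEAE |
| Mar 2022 | 20 Mar 2022 | TEAE | TEAE |
| Mar 2022 | missing | TEAE | TEAE |

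Only the first three rows change. In each the event was over two days before dosing, so it cannot satisfy the section 13.1 definition. The last two rows show that truly uncertain events remain TEAEs, so the intended caution is kept.

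**Step 4: how often the existing exception would help.** Assume the onset is known only to month and year, the true onset is equally likely on each of the 7 days before the first dose, and first-dose dates are spread evenly over 2021–2022. There are 730 × 7 = 5,110 combinations. The onset falls in the month before the first dose in 7 + 6 + 5 + 4 + 3 + 2 + 1 = 28 combinations per month, and 28 × 24 = 672 in all. The onset month therefore equals the first-dose month in (5,110 − 672) / 5,110 = 4,438 / 5,110 ≈ 87% of combinations, and there the exception does not operate. This figure is conditional on a month-only onset having been recorded; it does not say how often that happens.

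**Step 5: weight of one affected patient with no other TEAE in the category.** MP1032: 1/80 = 1.25 percentage points. Placebo: 1/40 = 2.5 percentage points.

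**The case against.** The strongest reply is that the definition in section 13.1 governs, and that section 8.3 is only a fallback for unknown onsets, openly labelled as conservative. On that view a sensible programmer would let a recorded stop date defeat the assumption, and such logic is often left to programming specifications. This has some force, and it limits the weight of the point. It does not remove it: section 8.3 states its exception in closed form, and the stop date is not in it.

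Four stronger readings are tempting, and the document does not support them.

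- *Sections 8.3 and 13.1 conflict.* They do not. Section 13.1 speaks only of missing onset dates. The exception in 8.3 concerns partial dates, and a wholly missing date has no partial date to consult.
- *Pre-dose AEs are to be expected.* The SAP plans for them in form: "Listings presenting all AEs including all episodes of one AE will be produced for TEAEs and non-TEAEs". That does not show that they will occur. Screening lasts at most 7 days and may fall on Day 1 itself (Table 1, note a). Note g to that table treats conditions arising up to first dosing as concomitant, under medical history. The pool of AEs that both start and end before dosing may be empty.
- *One such event could double an arm's count of related serious TEAEs.* This needs an AE that is serious, wholly pre-dose, without a usable onset date, with a recorded stop date and with blank causality, in a patient who was still randomized and dosed, plus exactly one true event in that arm. It is arithmetically possible but is not an estimate.
- *The 'related' imputation could trigger a stopping rule.* The rules in section 15 rest on relatedness as judged by the investigator, and the imputation applies to summary tables.

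It is also fair to say that the rule applies to both arms, that it can only over-count TEAEs, and that efficacy is untouched.

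**Conclusion.** The point holds as a minor defect. Followed literally, sections 8.3 and 13.1 class as treatment-emergent an AE that the recorded data show to have ended before the first dose, and as related if causality is blank. Section 13.1's own definition rules that out. This is a stated rule giving a wrong result in an identifiable case, not merely a missing detail, and section 9.5 already applies the corresponding end-date logic to medications.

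The effect is small. The SAP gives no count of affected events. If 0 to 3 patients among 120 are assumed, the addition ranges from nothing to 3/80 = 3.75 points if all are in the MP1032 arm, or 3/40 = 7.5 points if all are in the placebo arm. Very few or none is the likeliest outcome. These figures assume the planned arm sizes as denominators and that each patient has no other event in the category. Because listings keep the recorded dates, a reader could find such a case there, but the summary tables would still be wrong.

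**What to change.** Keep the current rule and add to sections 8.3 and 13.1: 'An AE with a missing or incomplete onset date whose stop date (complete, or partial where unambiguous) is before the first dose of study drug is not a TEAE.' State that a blank relationship is imputed as 'related' only after this check.

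Do not add wording that excludes an AE solely because it started before the first dose. Under section 13.1 worsening after initiation of study drug also makes an AE treatment-emergent, and such wording could drop a pre-dose event that worsened on treatment.

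The cost is one sentence in each of two sections and one programming condition. It should need no new data, since section 5.7 plans to summarize AE duration, which presupposes stop dates. It can be settled before database lock and unblinding.
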